## 9.4 WITHDRAWAL CRITERIA

If, during the clinical investigation, a subject must be prematurely withdrawn, the procedures outlined in this section must be followed. These procedures should not interfere with the initiation of any new treatments that are necessary to treat a subject's condition. Information on all withdrawn subjects will be documented.

Subjects may be withdrawn from the clinical investigation for any of the following reasons:

- a. Subject Withdrawal: A subject may voluntarily withdraw from the clinical investigation at any time and for any reason. The subject should be asked when possible, and without any form of coercion, the reason for his/her decision. If the participant withdraws from the clinical investigation completely, then data collected up until the point of withdrawal will be included in the final analysis. Subjects who decline to continue to take part will be given the opportunity to discuss/inform the research team of the reasoning behind their decision not to take part.
- b. Lost to Follow-Up (LTFU): A subject will be considered LTFU after all reasonable efforts have been made to contact the subject and request his/her continued participation in the clinical investigation. All attempts to contact the subject must be documented and should include at least two attempts to contact the subject by phone and one attempt via a certified letter. Data collected up until the point where the subject is LTFU will be included in the final analysis.

- c. Amputation: The discontinuation of a subject's participation in the clinical investigation due to Amputation (below the knee or above the knee) All available information concerning the amputation AEs should be provided. Data collected up until the point of amputation will be included in the final analysis.
- d. Adverse Event: The discontinuation of a subject's participation due to an AEs that prohibits his/her continued participation must be fully explained. All available information concerning the AEs should be provided. Data collected up until the point of AE will be included in the final analysis.

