4.2 Clinical Investigation Purpose

The Sponsor identified a need to collect PMCF data to verify the safety and efficacy/performance of the HOFFMANN® LRF SYSTEM, SALVATION™ EXTERNAL FIXATION SYSTEM, SALVATION™ FUSION BOLTS AND BEAMS, SALVATION™ 2 MIDFOOT NAIL, SALVATION™ 3DI PLATING SYSTEM, T2® ICF SYSTEM, and VALOR™ ANKLE FUSION NAIL Systems. The study was initiated to demonstrate the safety and performance/efficacy of these systems using the data collected. The study planned to assess efficacy through the 3-year amputation rate. Safety was to be assessed through the incidence of device-related intra-operative and post-operative adverse events/incidents (AEs) by 5 years. The study planned to follow all subjects annually post-operatively for 5 years.

5 Clinical investigation Objectives and Endpoints

The primary effectiveness hypothesis is that the 3-year amputation rate (including both above and below the knee) is less than the performance goal (PG).

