- Current mobility status (walking, use of mobility aids)

In addition, radiographic assessment of deformity correction was collected. The surgeon assessment of angle deformity correction based on radiograph will be summarized for the following:

- Meary's angle deformity: Lateral & AP;
- Talonavicular angle; and
- Cuboid height (mm)

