9.1 Primary Effectiveness/Performance Analysis

None of the subjects reached their three-year post-surgery follow-up. Thus, the three-year amputation rate, which is the primary endpoint will not be analyzed. Instead, the frequency of amputations at each post-surgery visit will be presented. The status of the subject at the latest follow-up, coded as either walking, use of mobility aids, bedridden or having amputation will be summarized instead.

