ADL Subscale					xx	xx.x ± xx.x	xx.x , xx.x	xx.x, xx.x	xx	xx.x ± xx.x	xx.x , xx.x	xx.x, xx.x

	Baseline				Final Visit				1 Yr. Visit			
	n	Mean ± SD	min,max	95% CI	n	Mean ± SD	min,max	95% CI	n	Mean ± SD	min,max	95% CI
Sports Subscale	xx	xx.x ± xx.x	xx.x, xx.x	xx.x, xx.x	xx	xx.x, xx.x	xx.x, xx.x	xx.x, xx.x	xx	xx.x ± xx.x	xx.x, xx.x	xx.x, xx.x
ADL Subscale	xx	xx.x ± xx.x	xx.x, xx.x	xx.x, xx.x	xx	xx.x, xx.x	xx.x, xx.x	xx.x, xx.x	xx	xx.x ± xx.x	xx.x, xx.x	xx.x, xx.x
SALVATION™ External Fixation												
FAAM SANE	xx	xx.x ± xx.x	xx.x, xx.x	xx.x, xx.x	xx	xx.x ± xx.x	xx.x, xx.x	xx.x, xx.x	xx	xx.x ± xx.x	xx.x, xx.x	xx.x, xx.x
Sports Subscale	xx	xx.x ± xx.x	xx.x, xx.x	xx.x, xx.x	xx	xx.x ± xx.x	xx.x, xx.x	xx.x, xx.x	xx	xx.x ± xx.x	xx.x, xx.x	xx.x, xx.x
ADL Subscale	xx	xx.x ± xx.x	xx.x, xx.x	xx.x, xx.x	xx	xx.x ± xx.x	xx.x, xx.x	xx.x, xx.x	xx	xx.x ± xx.x	xx.x, xx.x	xx.x, xx.x
Change from Baseline												
FAAM SANE					xx	xx.x ± xx.x	xx.x, xx.x	xx.x, xx.x	xx	xx.x ± xx.x	xx.x, xx.x	xx.x, xx.x
Sports Subscale					xx	xx.x ± xx.x	xx.x, xx.x	xx.x, xx.x	xx	xx.x ± xx.x	xx.x, xx.x	xx.x, xx.x
ADL Subscale					xx	xx.x ± xx.x	xx.x, xx.x	xx.x, xx.x	xx	xx.x ± xx.x	xx.x, xx.x	xx.x, xx.x

SANE -Single Assessment Numeric Evaluation.

Table 3.3 Surgeon Assessment

Device	Factors	1 Year Visit		Final Visit	
		N	%	N	%
SALVATION™ Fusion Bolts and Beams	Insulin Use				
	Yes	xx	xx.x%		
	No	xx	xx.x%		
	Ulcers	New Ulcer		Ulcer Healing	
	Yes	xx	xx.x%	xx	xx.x%
	No	xx	xx.x%	xx	xx.x%
	Chronic Ulcer				
	Yes	xx	xx.x%		
	No	xx	xx.x%		
	New Deep Infection				
	Yes	xx	xx.x%		
	No	xx	xx.x%		
	Ankle Alignment				
	Acceptable			xx	xx.x%
	Unacceptable			xx	xx.x%
	Not applicable			xx	xx.x%
	Current Status				
	Walking	xx	xx.x%	xx	xx.x%
	Mobility with aids	xx	xx.x%	xx	xx.x%
	Wheelchair	xx	xx.x%	xx	xx.x%
	Bed ridden	xx	xx.x%	xx	xx.x%
	Amputation	xx	xx.x%	xx	xx.x%
SALVATION™ Midfoot Nail	Insulin Use				
	Yes	xx	xx.x%		
	No	xx	xx.x%		
	Ulcers	New Ulcer		Ulcer Healing	
	Yes	xx	xx.x%	xx	xx.x%
	No	xx	xx.x%	xx	xx.x%
	Chronic Ulcer				
	Yes	xx	xx.x%		
	No	xx	xx.x%		
	New Deep Infection				
	Yes	xx	xx.x%		
	No	xx	xx.x%		
	Ankle Alignment				
	Acceptable			xx	xx.x%
	Unacceptable			xx	xx.x%
	Not applicable			xx	xx.x%
	Current Status				
	Walking	xx	xx.x%	xx	xx.x%
	Mobility with aids	xx	xx.x%	xx	xx.x%

Device	Factors	1 Year Visit		Final Visit	
		N	%	N	%
	Wheelchair	xx	xx.x%	xx	xx.x%
	Bed ridden	xx	xx.x%	xx	xx.x%
	Amputation	xx	xx.x%	xx	xx.x%
SALVATION™ 3Di Plating System	Insulin Use				
	Yes	xx	xx.x%		

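### SAP 9.1 and Table 3.3 make amputation one level of a mobility item, without recording its level on the limb, and the amputation count promised beside it has no table of its own

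*SAP*

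**What the plan says.** SAP 9.1 withdraws the planned primary analysis: "Thus, the three-year amputation rate, which is the primary endpoint will not be analyzed". Two summaries take its place. The first is a count: "Instead, the frequency of amputations at each post-surgery visit will be presented". The second is the subject's status at the latest follow-up, "coded as either walking, use of mobility aids, bedridden or having amputation will be summarized instead".

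SAP section 9, under surgeon assessment, describes the same item as "Current mobility status (walking, use of mobility aids" and names no amputation level there. The shell for Table 3.3 (SAP 15.1) has a Current Status block with five rows: Walking, "Mobility with aids", Wheelchair, Bed ridden and Amputation. Its columns are the 1 Year and Final visits.

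SAP section 5 fixes the scope of the event in the primary hypothesis: "the 3-year amputation rate (including both above and below the knee) is less than the performance goal (PG".

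On follow-up after the event, CIP 9.4 lists as a withdrawal reason "The discontinuation of a subject's participation in the clinical investigation due to Amputation (below the knee or above the knee", and adds: "Data collected up until the point of amputation will be included in the final analysis". SAP 6.3 repeats amputation at these two levels among the reasons for which withdrawal was allowed.

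**The concern.** Limb loss is an event that stays true once it has happened. Mobility is a state on the day of the visit. An amputee has a value on both, so a code that takes one value must drop one of them unless a rule says which prevails or allows several answers. Neither document gives such a rule. The amputation row also has no level, so it cannot separate the endpoint event from a toe or forefoot amputation.

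Amputation is what the study was set up to measure, and these two summaries are all that remains of the primary endpoint. If the count is in practice read off the Current Status block, it depends on which of two true boxes was ticked. The walking percentage may then mix preserved and amputated limbs.

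**Working it through.** The plan states no figure for this item, so there is none to reproduce. The check sets the passages side by side and then works out what one record weighs.

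**1. Levels of the status item**

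| Place | Mobility levels | Amputation | Level of amputation |
|---|---|---|---|
| SAP 9, surgeon assessment | walking, aids | not named | – |
| SAP 9.1 | walking, aids, bedridden | yes | none |
| Table 3.3, Current Status | walking, aids, wheelchair, bedridden | yes | none |

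The three lists differ. Wheelchair appears only in the shell.

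**2. Where the promised count could be printed**

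- List 14.1 has no amputation table, list 14.2 has no amputation or reoperation listing, and 14.3 plans no figures.
- Table 1.1 gives lost to follow-up, withdrawn consent, adverse event and other as discontinuation reasons. Amputation is not among them.
- Table 1.3 has a row for failures, and Table 4.1 has rows for device failure and for surgery. None of these names amputation.
- Table 3.3 names it, but has no 6-month column, whereas 9.1 promises every postoperative visit.

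The shells for Tables 4.2 and 4.3 are not in the text available, so this rests on the listed titles and the visible shells.

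**3. Records that fit two levels**

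- Below-knee amputation, still assessed, walking on a prosthesis: walking and amputation, under both 9.1 and Table 3.3.
- Above-knee amputation, still assessed, in a wheelchair: wheelchair and amputation, in Table 3.3 only.
- Toe amputation, walking: this does not meet the withdrawal criterion, so follow-up can continue. Walking applies, and amputation applies too because the row has no level.

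The first two can hide an endpoint event. The third can add an event that is not the endpoint.

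**4. Weight of one record**

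Input: about 42 implanted subjects (SAP 4.1). One record is 1/42 = 2.4 percentage points. The number of amputations k is not in the documents. The values below are assumptions that show the arithmetic, not expectations.

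| k assumed | k/42 | one coded by mobility, (k−1)/42 | one distal amputation added, (k+1)/42 |
|---|---|---|---|
| 1 | 2.4% | 0.0% | 4.8% |
| 2 | 4.8% | 2.4% | 7.1% |
| 4 | 9.5% | 7.1% | 11.9% |

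The visible Table 3.3 is laid out by device with no pooled block, so its denominators are smaller than 42. Numbers per device are not given. If the 42 were spread evenly over the seven systems with one system each, a row would hold 42/7 = 6 subjects and one record would weigh 1/6 = 16.7 points. Combined use of systems, which the CIP allows, would make rows larger.

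**The case against.** The strongest reply is that amputations are not lost. SAP 9.1 promises a separate count, and a correct count would not change however the status item is ticked. CIP section 14 collects amputation as a reoperation, CIP 9.4 asks for all available information on it, SAP 10.2 requires a narrative for each serious event, and Listing 12 lists adverse events. This stands. A reader might infer from the either/or code that amputations vanish from the study's reporting, and the documents do not support that. What remains is that the count has no visible table, so the only row into which it would naturally fall is the mixed one.

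Second, above- or below-knee amputation is a withdrawal reason and CIP data run to the amputation, so later prosthetic walking or wheelchair use should seldom be recorded. This also largely stands. But both documents make withdrawal possible rather than automatic, Table 3.3 provides an amputation row at both visits, and more distal amputations fall outside the criterion.

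Third, the case report form may allow several answers or record the worst state, and the order of the rows would suit the latter. That is possible. The form is not among the documents, and neither the SAP nor the CIP states such a rule.

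Fourth, all analysis is descriptive, so no test or decision depends on the code. This is correct and limits the weight of the point.

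**Conclusion.** The point holds as a defect of coding and table planning, modest in size. The status item mixes an event with mobility states, ignores the level that defines the endpoint, and differs between 9.1 and the shell. The amputation count promised beside it has no visible table. The amputation row or the mobility distribution in Table 3.3 can therefore be misclassified.

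Few records are likely to be affected. Each weighs 2.4 points on about 42 subjects and more within a device row. A reader might go further, apply the CIP's assumed 10% rate to 42 subjects, expect about four amputations and conclude that the table could understate them by half or more. The documents do not support this. The 10% is a 3-year rate, SAP 9.1 says nobody reached three years, no cell of the visible Table 3.3 has 42 as its denominator, and nothing indicates what share would be coded by mobility.

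The conclusion assumes that the form takes one answer, or that the table reports one answer per subject, and that the shells not available add no amputation table beyond the titles in list 14.1.

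**What to change.** In SAP 9.1 and Table 3.3, replace the single item by two variables.

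1. Amputation: cumulative yes/no with level, derived from the adverse-event, reoperation and disposition records rather than from the status tick. Above- and below-knee amputations count as the endpoint event; more distal ones go on a separate line.
2. Mobility: walking, aids, wheelchair, bedridden, without an amputation level and with the same levels in 9.1 and in the shell.

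Showing mobility separately for preserved and amputated limbs is optional at this sample size.

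The cost is a change of SAP wording, two shell rows and a hand check of a few forms. The source records are already collected under the CIP, and nothing in the treatment or follow-up of subjects changes.

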9.2 Analyses of Secondary Effectiveness Endpoints

EQ-5D-5L and FAAM scores will be summarized at each visit. In addition, score improvement at each post-operative visit will also be summarized by the change from baseline score in EQ-5D-5L and FAAM total and their component scores. Also, the post-operative physical and radiographic assessment of the surgical foot and the implant by the investigator will be summarized.

10 Safety Analyses

The safety data will be summarized by the frequency and percentage of AE incidence. Each AE was also assessed according to the relationship to the clinical investigation device and severity.

10.1 Adverse Events

The safety of each device will be summarized in the final report. The overall summary of adverse events will be presented for each device. Total events, patient counts and percentages of adverse events for each device will be summarized for the following factors:

- i.) Procedure-Related Adverse Event / Incident.
- ii.) Device-Related Adverse Event / Incident
- iii.) Device Failure
- iv.) Serious Adverse Event (SAE)
- v.) Hospitalization SAE Outcome
- vi.) Treatment Required for the AE

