### 9.1 INCLUSION CRITERIA

- a. Subject is a male or non-pregnant female age 18 years or older at the time of surgery;
- b. Subject is willing and able to give written informed consent and comply with the requirements of this Clinical Investigation Plan (CIP); and
- c. Subject has neuropathy and is intended to be treated for deformity with the one or a combination of the below Systems in accordance with the legally cleared/ approved IFU and Surgical Technique Manual.
  - HOFFMANN® LRF SYSTEM
  - SALVATION™ EXTERNAL FIXATION SYSTEM
  - SALVATION™ FUSION BOLTS AND BEAMS
  - SALVATION™ 2 MIDFOOT NAIL
  - SALVATION™ 3DI PLATING SYSTEM

- T2® ICF SYSTEM
- VALOR™ ANKLE FUSION NAIL SYSTEM

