## 11 Statistical Considerations

In general, the statistical analysis of will consider the combined outcome of all the devices under investigation. The population of the study will consist of all patients implanted with one or more of the devices listed Table 6.1. Subgroup analysis will be conducted for each device and device groups (i.e., devices for internal fixation only). The study required a sample size of 141 patients to provide at least 80% statistical power to reject the hypothesis that the 3-year amputation rate is less than the PG with a significance  $\alpha=0.05$ . The final statistical analysis will occur after all subjects have completed their 3-year anniversary. Secondary effectiveness endpoints include the total and component scores of the EQ-5D-5L and FAAM. Assessment of patient-reported outcome measure (PROM) improvement will be assessed at each planned study visit. The safety endpoints will include AEs, complications and secondary surgical intervention experienced by the patients. The device- and procedure- relatedness and severity of the safety endpoints will be assessed. The clinical and radiographic surgeon assessment of fusion and consolidation at 5 years will also be assessed.

Data will be captured via the EDC system. The data will be summarized descriptively at each pre-determined clinical visit. Quantitative factors will be summarized with mean, median, standard deviation and range minimum, maximum. Frequency and percentage will be computed for categorical factors. Survival analysis will be conducted to analyze time-to-event variables. Subjects without events will be censored at their last known event-free time point. Survival curves will be constructed using Kaplan-Meier estimates with confidence limits. A significance level ( $\alpha$ ) is 0.05 will be used for all tests of hypotheses

All statistical analysis will be performed using SAS version 9.4 or higher. A Statistical Analysis Plan (SAP) that contain the details of the analysis will be developed and finalized prior to the first anniversary of the first patient enrolled in the study.

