### 13.1 RELATIONSHIP TO THE DEVICE

The relationship of the AE to the study device or the implant procedure should be reported on the AE data collection form.

- Device Related: an AE that results from the presence or performance of the device.
- Procedure Related: an AE that occurs as a result of the implant procedure.

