4.1 Background and Rationale

This statistical analysis plan is developed to provide the analytic framework and the production of statistical output of the FIN Study. This analysis plan is based on the FINS CIP version 3, dated 27 April 2022. The FIN Study was a prospective, multisite, multiyear, post-market follow-up clinical (PMCF) investigation that aimed to compare the pooled three-year amputation rate of the investigational devices in **Table 1** to a performance goal derived from a literature-based source. The study planned to enroll at least 200 subjects at 10 sites in the US, however, the Sponsor decided to discontinue the enrollment on 28 October 2022. Approximately 42 subjects were implanted with at least one investigational device when the study was discontinued. This statistical plan will guide the statistical analysis and presentation of these subjects that were enrolled and implanted with any of the devices under investigation.

Table 1. Study Device FDA 510K Clearance Information

Device Name	Date of Clearance	510K Number
HOFFMANN® LRF SYSTEM	01Feb2021	K203568
SALVATION™ EXTERNAL FIXATION SYSTEM	06Jun2018	K180832
SALVATION™ FUSION BOLTS AND BEAMS	21Mar2014	K140741
SALVATION™ 2 MIDFOOT NAIL	11Jul2018	K180024
SALVATION™ 3DI PLATING SYSTEM	22May2014	K140792
SALVATION™ OSTEOPENIC SCREW	14May2014	K140408
T2® ICF SYSTEM	20Mar2020	K193366
VALOR™ ANKLE FUSION NAIL	22Oct2014	K142602

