6.2 Inclusion-Exclusion Criteria

Subjects that met the following inclusion criteria were invited to be enrolled in the study.

- a. Subject was a male or non-pregnant female age 18 years or older at the time of surgery;
- b. Subject was willing and able to give written informed consent and comply with the requirements of the Clinical Investigation Plan (CIP); and
- c. Subject had neuropathy and intended to be treated for deformity with the one or a combination of the below Systems in accordance with the legally cleared/ approved IFU and Surgical Technique Manual.
 - o HOFFMANN® LRF SYSTEM
 - o SALVATION™ EXTERNAL FIXATION SYSTEM
 - o SALVATION™ FUSION BOLTS AND BEAMS
 - o SALVATION™ 2 MIDFOOT NAIL
 - o SALVATION™ 3DI PLATING SYSTEM
 - o T2® ICF SYSTEM
 - o VALOR™ ANKLE FUSIO NAIL SYSTEM

Subjects that were

- a. determined, by the investigator, to be an inappropriate candidate for the procedure indicated; or
- b. unable to consent to participate (written, informed consent); or
- c. unable to attend/complete the requested follow-up visits

were excluded from the study

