Talonavicular Meary's Angle	xx	xxx	xx	xx	xx	(xxx,xxx)	xx	xx	xx	xx	xx	(xx,xx,xxx)	xx	xx	xx	xx	xx	(xx,xx,xxx)
Cuboid height (mm)	xx	xxx	xx	xx	xx	(xxx,xxx)	xx	xx	xx	xx	xx	(xx,xx,xxx)	xx	xx	xx	xx	xx	(xx,xx,xxx)
SALVATION™ MIDFOOT NAIL																		
AP Meary's Angle	xx	xxx	xx	xx	xx	(xxx,xxx)	xx	xx	xx	xx	xx	(xx,xx,xxx)	xx	xx	xx	xx	xx	(xx,xx,xxx)
Lateral Meary's Angle	xx	xxx	xx	xx	xx	(xxx,xxx)	xx	xx	xx	xx	xx	(xx,xx,xxx)	xx	xx	xx	xx	xx	(xx,xx,xxx)
Talonavicular Meary's Angle	xx	xxx	xx	xx	xx	(xxx,xxx)	xx	xx	xx	xx	xx	(xx,xx,xxx)	xx	xx	xx	xx	xx	(xx,xx,xxx)
Cuboid height (mm)	xx	xxx	xx	xx	xx	(xxx,xxx)	xx	xx	xx	xx	xx	(xx,xx,xxx)	xx	xx	xx	xx	xx	(xx,xx,xxx)
Valor™ Nail																		
AP Meary's Angle	xx	xxx	xx	xx	xx	(xxx,xxx)	xx	xx	xx	xx	xx	(xx,xx,xxx)	xx	xx	xx	xx	xx	(xx,xx,xxx)
Lateral Meary's Angle	xx	xxx	xx	xx	xx	(xxx,xxx)	xx	xx	xx	xx	xx	(xx,xx,xxx)	xx	xx	xx	xx	xx	(xx,xx,xxx)
Cuboid height (mm)	xx	xxx	xx	xx	xx	(xxx,xxx)	xx	xx	xx	xx	xx	(xx,xx,xxx)	xx	xx	xx	xx	xx	(xx,xx,xxx)
Talonavicular Meary's Angle	xx	xxx	xx	xx	xx	(xxx,xxx)	xx	xx	xx	xx	xx	(xx,xx,xxx)	xx	xx	xx	xx	xx	(xx,xx,xxx)

FINS (US20-SAL-001)

Table 4.1 Summary of All Adverse Events

SALVATION™ Fusion Bolts and Beams (N = xx)		SALVATION™ MIDFOOT NAIL (N = xx)		SALVATION™ External Fixation (N = xx)		SALVATION™ 3D Plating System (N = xx)		VALOR™ Nail (N = xx)	
Subjects	Event	Subjects	Event	Subjects	Event	Subjects	Event	Subjects	Event
xx(xx.x%)	xx	xx(xx.x%)	xx	xx(xx.x%)	xx	xx(xx.x%)	xx	xx(xx.x%)	xx
Total									
Procedure-Related	xx(xx.x%)	xx	xx(xx.x%)	xx	xx(xx.x%)	xx	xx(xx.x%)	xx	xx(xx.x%)
Device-Related	xx(xx.x%)	xx	xx(xx.x%)	xx	xx(xx.x%)	xx	xx(xx.x%)	xx	xx(xx.x%)
Device Failure	xx(xx.x%)	xx	xx(xx.x%)	xx	xx(xx.x%)	xx	xx(xx.x%)	xx	xx(xx.x%)
UADE	xx(xx.x%)	xx	xx(xx.x%)	xx	xx(xx.x%)	xx	xx(xx.x%)	xx	xx(xx.x%)
Unanticipated AE	xx(xx.x%)	xx	xx(xx.x%)	xx	xx(xx.x%)	xx	xx(xx.x%)	xx	xx(xx.x%)
Serious AE	xx(xx.x%)	xx	xx(xx.x%)	xx	xx(xx.x%)	xx	xx(xx.x%)	xx	xx(xx.x%)
Hospitalization	xx(xx.x%)	xx	xx(xx.x%)	xx	xx(xx.x%)	xx	xx(xx.x%)	xx	xx(xx.x%)
Death	xx(xx.x%)	xx	xx(xx.x%)	xx	xx(xx.x%)	xx	xx(xx.x%)	xx	xx(xx.x%)
Required Treatment**	xx(xx.x%)	xx	xx(xx.x%)	xx	xx(xx.x%)	xx	xx(xx.x%)	xx	xx(xx.x%)
Physical Therapy	xx(xx.x%)	xx	xx(xx.x%)	xx	xx(xx.x%)	xx	xx(xx.x%)	xx	xx(xx.x%)
Medication	xx(xx.x%)	xx	xx(xx.x%)	xx	xx(xx.x%)	xx	xx(xx.x%)	xx	xx(xx.x%)
Surgery	xx(xx.x%)	xx	xx(xx.x%)	xx	xx(xx.x%)	xx	xx(xx.x%)	xx	xx(xx.x%)
Other	xx(xx.x%)	xx	xx(xx.x%)	xx	xx(xx.x%)	xx	xx(xx.x%)	xx	xx(xx.x%)

Table 4.2 Device-related Adverse Events

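### SAP 10.1 and Table 4.1 report adverse events only by device, in columns that can overlap and omit two systems, so the table gives no study-level rate

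*SAP*

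**What the plan says.** Combination treatment is part of the design. Protocol 9.1 admits a subject who is "intended to be treated for deformity with the one or a combination of the below Systems", and SAP 6.2 repeats the criterion. Protocol 9.3 lists the implanted systems with and/or. Protocol 11 defines the population: "The population of the study will consist of all patients implanted with one or more of the devices listed Table 6.1".

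The protocol's analysis is mainly pooled. Protocol 11 says that the analysis in general "will consider the combined outcome of all the devices under investigation", with device subgroups in addition. Protocol 11.2.4 covers all enrolled subjects and promises, for each type of event, total counts and per-subject rates with exact binomial 95% intervals.

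The SAP was written after enrolment stopped: "Approximately 42 subjects were implanted with at least one investigational device when the study was discontinued" (SAP 4.1). SAP 7.2 defines one safety population of everyone who received any device. SAP 10.1 then sets the reporting unit: "Total events, patient counts and percentages of adverse events for each device will be summarized for the following factors". The shell headed "Table 4.1 Summary of All Adverse Events" has columns for Fusion Bolts and Beams, Midfoot Nail, External Fixation, 3Di Plating and VALOR Nail, each with its own N. The word Total in that shell labels a row. SAP 12 states that the analysis planned in the protocol is unchanged.

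On attribution, Protocol 13.1 says: "The relationship of the AE to the study device or the implant procedure should be reported on the AE data collection form". It does not say whether the particular system is to be named.

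**The concern.** When treatments can be combined, device columns are not separate groups. A subject with beams and an external fixator could belong in two columns, and the SAP does not say whether that subject appears in both, in one chosen by some convention, or elsewhere. A reader who adds the columns may count some subjects more than once. A subject treated only with HOFFMANN LRF or T2 ICF has no column at all.

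What is at stake is the main safety result of a study that stopped early: how many of the roughly 42 subjects had an adverse event of each kind. The protocol planned that figure, and Table 4.1 does not give it. The same question arises for amputation, because SAP 9.1 replaces the pooled 3-year rate with amputation frequency by visit and latest status.

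**Working it through.** Neither document gives an adverse event rate or a number of multi-system subjects, so there is no stated figure to reproduce. The check compares the passages, then works out what overlap would do under assumed counts.

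**Passages side by side**

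1. Overlap is allowed by Protocol 9.1, 9.3 and 11 and by SAP 6.2.
2. Table 4.1 has no column with the safety population as denominator. Other parts of the SAP do plan overall figures: SAP 8.1 promises disposition by device and overall, Table 1.4 has an all-subjects row, and Table 1.6 has an all-subjects column. The gap in Table 4.1 therefore looks like an omission.
3. The columns are not exhaustive. Table 1.1 lists seven systems and Table 4.1 lists five.
4. No visible text assigns a multi-system subject or event to a column.
5. Early termination is the SAP's stated reason for descriptive analysis without hypothesis tests (SAP 7). It does not explain the loss of a descriptive pooled rate with an interval.
6. The visible shell of Table 3.3, which holds the amputation status rows, covers four systems and has no total. Protocol 11.2.2 defines the primary endpoint as a pooled rate.

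**Size of a possible overlap**

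Inputs: N = 42 (SAP 4.1, approximate). Assumed: c subjects have exactly two systems, every system used has a column, and two-system subjects are counted in both columns. Also assumed, for illustration only: 20% of single-system and 50% of two-system subjects have an event.

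- Sum of column Ns = 42 + c.
- True pooled rate = [(42 − c) × 0.20 + c × 0.50] / 42.
- Rate from adding columns = [(42 − c) × 0.20 + 2c × 0.50] / (42 + c).

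| c | Sum of Ns | True pooled rate | Rate from adding columns |
|---|---|---|---|
| 0 | 42 | 20.0% | 20.0% |
| 7 | 49 | 25.0% | 28.6% |
| 14 | 56 | 30.0% | 35.0% |
| 21 | 63 | 35.0% | 40.0% |
| 28 | 70 | 40.0% | 44.0% |

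If both groups have the same rate, say 30%, the rate from adding columns stays at 30%. The summed count of subjects with an event is still too high, by (42 + c)/42: 1.17, 1.33, 1.50 and 1.67 times for c = 7, 14, 21 and 28.

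**Can the pooled rate be read from the table?**

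Take c = 21 and suppose the columns show 15 subject entries with an event. If k of those subjects have two systems, the number of different subjects is 15 − k, with 2k ≤ 15, so k runs from 0 to 7. The answer lies between 8/42 = 19.0% and 15/42 = 35.7%, and the table cannot narrow it. With c = 0, 15 entries are 15 subjects.

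**What an all-subjects column would show**

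The exact 95% interval at N = 42 is 0 to 8.4% for no subjects with an event, and 12.1% to 39.5% for 10 subjects (10/42 = 23.8%).

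**The case against.** The strongest reply is that the data remain accessible. The SAP defines a pooled safety population and plans an adverse event listing (Listing 12), a separate summary of serious events and a narrative for each. With about 42 subjects, someone could count different subjects and events from the listing. This stands: a reader might infer that no pooled rate can be recovered from the study, and the documents do not support that. The supportable statement is that Table 4.1 does not give one and SAP 10.1 does not plan one.

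Three further limits also stand.

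- A reader might infer that multi-system subjects and their events are counted under every device. The SAP does not say so. Assignment to a single device is equally compatible with its text, and the defect is the missing rule.
- A reader might infer that all adverse event tables are by device only. The shells of Tables 4.2 and 4.3 are not visible, so the point is confined to SAP 10.1 and Table 4.1.
- A reader might take a rate among all recipients of a device to be wrong because some had other systems too. It is a valid rate for those recipients if labelled as such. A higher rate in combination subjects could also reflect a more severe deformity. Splitting about 42 subjects into mutually exclusive columns is a preference and would leave very small groups.

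It can also be argued that SAP 12 leaves Protocol 11.2.4 in force, so the pooled rates are still planned. On that reading the Table 4.1 shell fails to implement the plan, and the remedy is the same. Nor does the singular wording of Protocol 13.1 show that the adverse event form cannot identify the system, because the form is not in the documents.

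**Conclusion.** The point holds as a reporting defect. SAP 10.1 and the visible Table 4.1 shell give device-level figures in columns that may overlap and that omit two study systems. They contain no study-level rate and no assignment rule. This departs from Protocol 11 and 11.2.4, while SAP 12 declares no change.

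The size of any distortion cannot be stated, because the number of multi-system subjects is not given. It is nil if there are none. The worked ranges rest on assumed numbers of two-system subjects, counting in both columns and, in the table of rates, assumed event rates. The absence of a study-level column and of the two device columns depends on none of these assumptions. All analyses are descriptive, so no test or formal conclusion is affected.

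**What to change.** In SAP 10.1 and Table 4.1:

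- Add an all-subjects column, with N equal to the safety population (about 42), that counts each subject and each event once and carries the exact 95% intervals of Protocol 11.2.4.
- Add columns for HOFFMANN LRF and T2 ICF.
- State in a footnote that each device column shows all recipients of that device, that the columns are not mutually exclusive and that they must not be summed. Give the number of multi-system subjects in each.
- Where the adverse event record identifies the related system, count a device-related event under that system. Otherwise label it as device not distinguishable.

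Add the same all-subjects total to the amputation and current-status rows of Table 3.3. If the sponsor prefers not to restore the pooled rates and intervals, SAP 12 should record the departure from the protocol.

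The cost is a few extra columns, a footnote and some SAP wording. No new data collection is needed, since events that cannot be attributed are labelled as such.
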